6.2 Data Sharing Plans

6.2.1 Human Data Sharing Plan

What data will be shared?

I will share human data generated in this research for future research as follows:

- De-identified data in an NIH-funded or approved public repository.
- De-Identified data in BTRIS (automatic for activities in the Clinical Center)
- De-identified or identified data with approved outside collaborators under appropriate agreements.

How and where will the data be shared?

Data will be shared through:

- An NIH-funded or approved public repository. Insert name or names: clinicaltrials.gov .
- BTRIS (automatic for activities in the Clinical Center)
- Approved outside collaborators under appropriate individual agreements.
- Publication and/or public presentations.

When will the data be shared?

- Before publication.
- At the time of publication or shortly thereafter.

6.2.2 Genomic Data Sharing Plan

No genomic data will be gathered as part of this study.

6.3 Response Criteria

For the purposes of this study, patients should be re-evaluated for response per the study calendar (3.4). In addition to a baseline scan, confirmatory scans should also be obtained not less than 4 weeks following initial documentation of objective response.

Responses will be assessed using both serum calcitonin levels and imaging using Immune Related Response Criteria below.

6.3.1 Serum Calcitonin

For calcitonin, response assessment, the baseline calcitonin value will be established prior to treatment. If multiple values have been obtained, the most recent value will be considered the baseline unless the primary investigator feels that the value is unreliable. In this case a note will document the reason for not using that value at enrollment and identification of an alternative baseline (obtained within 8 weeks of enrollment) will be used.

In order to be considered to have a “Calcitonin Response” patients must have a $\geq 50\%$ decline from designated baseline value that is then confirmed on a subsequent serum calcitonin assessment at least one week later.

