2.5 Baseline Evaluation

Screening evaluations performed within 8 weeks prior and within 10 days prior to treatment initiation will be used as baseline.

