3.3 Drug Administration

Trial treatment should be administered on Day 1 of each cycle after all procedures/assessments have been completed as detailed on the Study Calendar (Section 3.4). Trial treatment may be administered up to 7 days before or after the scheduled Day 1 of each cycle due to administrative reasons.

All trial treatments will be administered on an outpatient basis.

Pembrolizumab 200 mg will be administered as a 30 minute IV infusion every 3 weeks. Every effort should be made to target infusion timing to be as close to 30 minutes as possible.

However, a window of -5 minutes and +10 minutes is permitted (i.e., infusion time is 30 minutes: -5 min/+10 min). Premedication for patients who experience an infusion reaction should be administered 60 minutes (+/- 30 minutes) prior to the infusion.

The Pharmacy Manual contains specific instructions for the preparation of the pembrolizumab infusion fluid and administration of infusion solution. Pembrolizumab is administered through a 0.2 to 5 micron sterile, nonpyrogenic, low-protein binding inline or add-on filter. Do not infuse other medications through the same infusion line.

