3.4 Study Calendar

Procedure	Screening/ Baseline ⁵	Treatment Cycles (21 days +/- 7 days) ¹								Cycle 9 and beyond	Post Treatment ⁶	
		C1 D1	C2 D1	C3 D1	C4 D1	C5 D1	C6 D1	C7 D1	C8 D1			
History and PE	X ²	X	X	X	X	X	X	X	X	X	X	X
Vital signs	X ²	X	X	X	X	X	X	X	X	X	X	X
Performance Score	X ²											
Height/Weight	X ³											
HIV, Hep B, C	X											
Pregnancy Test (Urine or Serum beta-HCG)	X ²											
UA ⁴	X ²											
PT/INR and PTT	X ²											
Chemistries ⁷	X ²	X	X	X	X	X	X	X	X	X	X	X
CBC	X ²	X	X	X	X	X	X	X	X	X	X	X
TSH	X ²			X	X	X	X	X	X	X	X	X
T/B/NK subsets	X ²	X	X	X	X	X	X	X	X	X	X	X
Tumor Markers: Calcitonin and CEA	X ²	X	X	X	X	X	X	X	X	X	X	X
Correlative Research Studies (research bloods see Appendix B)	X	continue at 3 month intervals									X ⁸	
Radiological Assessments (MRI or CT Neck, Ch/Abd/Pelvis, Bone Scan) ³	X	continue at 3 month intervals										
EKG ³	X	continue at 3 month intervals									X	
Biopsy (optional) ⁸												
Adverse Events		X										
Concomitant Medications		X										

¹ If patient is delayed, subsequent infusion must be at least 18 days later

Abbreviated Title: Pembrolizumab in MTC

Version Date: 3/26/18

² Must be done within 10 days prior to initiation of study therapy

³ Must be done within 8 weeks prior to initiation of study therapy, and then will be done every 3 months while patients remain on study

⁴ May be omitted if patient is incontinent and cannot provide a urine sample

⁵ Baseline/Screening requirements may also be used for Day 1 requirements if logistically necessary

⁶ Post-Therapy Assessment done 3 weeks after last treatment when logistically feasible (with a possible extension to 4 weeks if logistically necessary). Patients will be offered enrollment in the 04-C-0274 "Follow-Up Study of Subjects Previously Enrolled in Immunotherapy Studies Utilizing Gene Transfer or other Immunotherapeutic Agents" once off study.

⁷ Chemistries: sodium, potassium, chloride, CO₂, creatinine, glucose, BUN, albumin, calcium, magnesium, phosphorus, alkaline phosphatase, ALT, AST, total bilirubin, direct bilirubin, LD, total protein, total CK, uric acid

⁸ When logistically feasible, pre-treatment and post-treatment samples may be obtained from consenting patients.

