6.3.2 Imaging

Immune Related Response Criteria

Because of direct clinical observations of immune cell influx into tumor causing enlargement in some patients prior to sustained response, recently it has been suggested that clinical trials involving the use of immunotherapy use alternative guidelines, called immune related response criteria (irRC) to determine radiographic response or progression after therapy²². These recommendations have been used in recent clinical trials. One study of 227 subjects with metastatic melanoma showed that the approximately 10% of patients who had PD by modified WHO criteria but either of CR, PR or SD by irRC had a similar overall survival as those patients who had SD, PR or CR by both criteria. The irRC was created using bidimensional measurements (as previously widely used in the WHO criteria). We have taken the concepts of the irRC and combined them with the recently revised RECIST 1.1²³ to come up with the modified irRC used in this protocol. Consistent with the irRC, the main changes from RECIST 1.1 are (a) a requirement for confirmation of both progression and response by imaging at least 4 weeks after initial imaging and (b) not automatically calling the appearance of new lesions progressive disease if the total measurable tumor burden has not met criteria for progressive disease.

For immune-related response criteria (irRC), only index and measurable new lesions are taken into account. At baseline tumor assessment on this trial, target lesions will be measured along the longest axis and the measurements will be summed, called sum of largest diameter (SLD). These lesions must be a minimum of 10mm per lesion, maximum of 5 target lesions, maximum of 2 per organ system. At each subsequent tumor assessment, the unidimensional measurement of target lesions and of new measureable lesions are added together to provide the total tumor burden: As per the modified definitions below, all responses and progression except stable

disease (SD) require confirmation on a consecutive scan at least 4 weeks from the initial observation).

Definitions of irRC:

Response	irRC
New measurable lesions	Incorporated into tumor burden
New non-measurable lesions	Do not define progression (but precludes irCR)
Non-index lesions	Contributes to defining irCR (complete disappearance required)

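### Averaging the two scheduled pre-dose calcitonin values would be a cheap improvement on a baseline that now rests on a single draw

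*Combined protocol and SAP*

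**What the plan says.** The study calendar (section 3.4) marks the row "Tumor Markers: Calcitonin and CEA" at screening, at Cycle 1 Day 1 (C1D1) and at every later cycle. Its footnote 2 places the screening draw within 10 days before treatment. Section 3.3 puts the C1D1 draw before the infusion: "Trial treatment should be administered on Day 1 of each cycle after all procedures/assessments have been completed as detailed on the Study Calendar". Two pre-dose values are therefore planned. Footnote 5 allows an exception: "Baseline/Screening requirements may also be used for Day 1 requirements if logistically necessary". Some patients may thus have only one.

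Section 6.3.1 picks a single value: "If multiple values have been obtained, the most recent value will be considered the baseline". The investigator may set that value aside as unreliable: "In this case a note will document the reason for not using that value at enrollment". An alternative from within 8 weeks of enrollment then takes its place. Section 2.5 has a general sentence for all screening tests: "Screening evaluations performed within 8 weeks prior and within 10 days prior to treatment initiation will be used as baseline". A calcitonin response is a fall of at least 50% from baseline "that is then confirmed on a subsequent serum calcitonin assessment at least one week later".

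Section 8 sets the mark at 4 of 15 patients per cohort. It gives a 5.6% chance of reaching the mark at a true rate of 10%, and 90.9% at 40%.

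**The concern.** Error in the baseline enters every later comparison for that patient. If the one chosen value is high by chance, all later draws look like declines. Confirmation does not protect against this, because the confirming draw is compared with the same baseline. A chance low value hides a true decline in the same way. The plan already collects a second pre-dose value in most patients and does not use it.

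Calcitonin response is one of two routes to the primary endpoint, and each cohort is read against 4 of 15, so one or two reclassified patients can move the reading. Sections 2.5 and 6.3.1 also point to different draws when both exist.

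**Working it through.** **The plan's own figures.** Exact binomial, n = 15: P(X ≥ 4 | p = 0.10) = 5.56% and P(X ≥ 4 | p = 0.40) = 90.95%. Both agree with section 8. The proposal changes how a responder is classified, so these figures stay as they are.

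**Inputs from the documents.** Two pre-dose draws; a draw every 3 weeks; treatment for 2 years; a 50% threshold; confirmation at least one week later. I use 8 draws (24 weeks) and 17 draws (about a year: 52/3 ≈ 17).

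**Assumed, because the documents are silent.** Lognormal within-patient noise with CV 15–30%; independent draws, or a correlation of 0.5 between adjacent draws; no early discontinuation, which would lower all rates.

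**Effect on noise.** With s = √ln(1 + CV²), the SD of log(post/baseline) is s√2 for one baseline value and s√1.5 for the geometric mean of two. The ratio is √0.75 = 0.87, a 13% reduction. At CV 20%, s√2 = 0.280 and s√1.5 = 0.243. The chance that a single draw in a flat marker shows a 50% fall is Φ(ln 0.5/0.280) = 0.67%, against Φ(ln 0.5/0.243) = 0.21%.

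**False confirmed response, flat marker, 17 draws, any later draw confirming** (simulation, 200,000 patients per setting; repeat runs differ by up to about 0.2 points):

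| CV | One value | Geometric mean |
|---|---|---|
| 15% | 0.1% | 0% |
| 20% | 2.2% | 0.4% |
| 25% | 8.4% | 3.5% |
| 30% | 16.7% | 10.2% |

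Sensitivity of the CV 25% row:
- Correlation 0.5: 7.5% to 5.5%.
- Confirmation taken to mean the next draw: 3.3% to 0.9%.
- 8 draws: 3.9% to 1.2%.

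**Detection of true declines.** For a decline of exactly 50%, CV drops out. With one baseline value and k draws, the patient responds unless the baseline draw's noise ranks lowest or second lowest of k + 1 exchangeable values, so P = (k − 1)/(k + 1). That is 7/9 = 78% at 8 draws and 16/18 = 89% at 17. The geometric mean gives 84% and 95% by simulation. For a true 60% decline at CV 25%, detection goes from 94% to 98% (8 draws) and from 98% to 99.7% (17 draws).

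**Cohort level**, CV 25%, 8 draws, any later draw confirming. Rate = share truly falling by 60% × detection + remainder × false-response rate.
- 40% truly falling: 0.40 × 0.943 + 0.60 × 0.039 = 0.401, so P(≥ 4 of 15) = 91.0%. With averaging, 0.40 × 0.980 + 0.60 × 0.012 = 0.399, giving 90.9%.
- 10% truly falling: 0.10 × 0.943 + 0.90 × 0.039 = 0.129, giving 12.0%. With averaging, 0.10 × 0.980 + 0.90 × 0.012 = 0.109, giving about 7%.

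**Downside.** With any later draw confirming, averaging calls more true 40% declines responses (17 draws, CV 25%: 70% to 76%).

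**The case against.** The last pre-treatment value is a legitimate, pre-stated baseline, and averaging is a design preference. That stands, and it is why this is an improvement and not a correction.

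A reader might infer that sections 2.5 and 6.3.1 contradict each other so badly that the endpoint is undefined. The documents do not support that. Section 2.5 speaks of all screening tests, while 6.3.1 is specific to calcitonin and expressly covers several values. Where footnote 5 applies there is only one value and no conflict. What is missing is a cross-reference. For a true decline of exactly 50%, screening and C1D1 baselines disagree on responder status in 31% of patients (8 draws), but that is a knife-edge case. At a true 60% decline and CV 25% they disagree in about 10%.

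A reader might also infer that false responses undermine the 5.6%. That needs a within-patient CV, which the documents do not give. At CV 15% the effect is almost nil. A marker doubling every 2 years gives only 2.6% with the present rule (CV 25%, 17 draws). The remark in section 1.1.1 that a confirmed 50% decline would be rare is weak evidence for the low end. The larger figures also let any later draw confirm, whereas the wording of 6.3.1 fits the next draw equally well.

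Finally, because imaging responses "require confirmation on a consecutive scan at least 4 weeks from the initial observation", a reader might want calcitonin confirmed at the next available draw too. That is a sensitivity–specificity trade-off. On its own it lowers detection of an exact 50% decline from 78% to 65% (8 draws). Added to averaging, it takes cohort power from 91.0% to 87.5% (8 draws, CV 25%).

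**Conclusion.** The point holds as a cheap improvement. Two pre-dose values are scheduled, one is used, and averaging them removes 13% of the noise SD in the log ratio if draws are independent. Over an assumed CV of 20–30% (independent noise, 17 draws, any later draw confirming), false responses in a flat marker fall by 1.8 to 6.5 percentage points. The gain is smaller with serial correlation, almost nil at CV 15%, and absent in patients with only one pre-dose value, whose number is unknown. Averaging also improves detection of true 50–60% declines and leaves cohort power essentially unchanged at 8 draws.

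Nothing here shows the design figures in section 8 or the existing baseline rule to be wrong. A pilot that also reports actual decline percentages and a confidence interval lets readers see borderline cases, which lowers the stakes further.

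**What to change.** In section 6.3.1, state: *Baseline calcitonin is the geometric mean of the values drawn within 10 days before dose 1 (screening and C1D1 where both exist, otherwise the single value).* Keep the present note rule, so that a value set aside with a documented reason is left out of the mean, and keep the 8-week alternative for the case where none remains. In section 2.5, add: *For calcitonin, baseline is as defined in 6.3.1.*

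Use the geometric mean, not the arithmetic mean. At CV 40% over 34 draws, with any later draw confirming, the arithmetic mean gives slightly more false responses than one value (48% against 45%), while the geometric mean gives 44%.

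The cost is two sentences: no new samples, and no change to n, the 4-of-15 mark or the stated probabilities. The price in performance is the modest rise in true 40% declines called responses. A next-draw confirmation rule is not part of this change.

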3.2 Trial Treatments

The treatment to be used in this trial is outlined below in **Table 3**

Table 3 Trial Treatment

Drug	Dose/Potency	Dose Frequency	Route of Administration	Regimen/Treatment Period	Use
Pembrolizumab	200 mg	Q3W	IV infusion	Day 1 of each 3 week cycle	Experimental
Treatment Duration with Pembrolizumab: 2 years (3 week intervals)					

Trial treatment should begin on the day of enrollment or as close as possible to that date.

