7.4 Data and Safety Monitoring Plan

7.4.1 Principal Investigator/Research Team

The clinical research team will meet on a regular basis at least monthly when patients are being actively treated on the trial to discuss each patient. Decisions about dose level enrollment and dose escalation if applicable will be made based on the toxicity data from prior patients.

All data will be collected in a timely manner and reviewed by the principal investigator or a lead associate investigator. Adverse events will be reported as required above. Any safety concerns, new information that might affect either the ethical and or scientific conduct of the trial, or protocol deviations will be immediately reported to the IRB using iRIS.

The principal investigator will review adverse event and response data on each patient to ensure safety and data accuracy. The principal investigator will personally conduct or supervise the investigation and provide appropriate delegation of responsibilities to other members of the research staff.

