8 STATISTICAL CONSIDERATIONS

The primary objective of this trial is to determine whether administering a PD1 inhibitor to patients with medullary thyroid cancer will permit a modest fraction to be able to experience a 50% or greater decline in calcitonin levels or experience a clinical response by partial/complete response on imaging.

Patients on this trial will be enrolled into two cohorts: patients who have previously received vaccine and patients who have not previously received vaccine. The results from each cohort will be considered individually.

In each cohort, the trial will be conducted as a single stage pilot trial of 15 evaluable patients. It is expected that this regimen will result in a limited fraction of patients who experience a 50% or greater decline in calcitonin levels or experience a clinical response by partial/complete response on imaging. If the true probability that patients will experience a 50% decline in calcitonin or respond is 10%, there is only 5.6% probability of having 4 or more of 15 do so, while if the true probability is 40% or more, there is 90.9% or greater probability of observing 4 or more who experience this decline or respond. Thus, observing 4 or more with this decline or a response in a cohort is more likely to be associated with a modest fraction with 50% or greater decline in calcitonin levels or respond than if fewer patients in a cohort experience this decline or respond.

A 95% confidence interval will also be formed about the observed proportion of patients who experience a 50% or greater decline or respond, and the actual decline percentages for patients

on both cohorts will be reported descriptively, as well as the fraction who experience a clinical response. With limited numbers of patients in this trial, there will be low power to do a formal comparison of the two cohorts; information about the proportion with substantial declines or responses in either cohort may be used to guide development of future trials using this approach.

It is anticipated that 1 patient per month may enroll onto this trial. Thus, to obtain 30 evaluable patients, approximately 2 to 3 years of accrual is anticipated. In order to allow for a small number of inevaluable patients, the accrual ceiling will be set to 32 patients.

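### Section 6.3.1 lets the investigator replace the calcitonin baseline on impression alone, with no objective ground, no rule for the replacement and no dated lock

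*Combined protocol and SAP*

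**What the plan says.** The calcitonin half of the primary endpoint is a fall of at least 50% from one designated baseline, confirmed at least a week later (Section 6.3.1). On that baseline the section says four things:

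- Timing: "the baseline calcitonin value will be established prior to treatment".
- Default and exception: where several values exist, "the most recent value will be considered the baseline unless the primary investigator feels that the value is unreliable".
- Record: an override requires a note giving the reason.
- Replacement: "identification of an alternative baseline (obtained within 8 weeks of enrollment) will be used".

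Other sections bear on it. Section 2.5 names the screening evaluations as baseline. The calendar in Section 3.4 schedules calcitonin at screening (within 10 days before treatment), on cycle 1 day 1 and at every later cycle; its footnote 5 lets screening values stand in for day 1. Section 3.2 says: "Trial treatment should begin on the day of enrollment or as close as possible to that date". The trial is open label (Section 3.1), and under Section 7.4.1 "The principal investigator will review adverse event and response data on each patient".

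Section 8 judges each cohort separately: "the trial will be conducted as a single stage pilot trial of 15 evaluable patients". If the true rate "is 10%, there is only 5.6% probability of having 4 or more of 15 do so", and "if the true probability is 40% or more, there is 90.9% or greater probability of observing 4 or more". It says nothing about how the baseline is chosen.

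**The concern.** The baseline is the divisor in every percentage decline, so a higher baseline makes the same on-treatment value look like a larger fall. Take an on-treatment value of 600. Against a baseline of 1,000 the decline is 1 − 600/1,000 = 40%, not a response. Against 1,250 it is 1 − 600/1,250 = 52%, a response.

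The only stated ground for setting the default aside is the investigator's impression. No specimen, assay or laboratory criterion is listed, and nothing says which value to take when several are available. The replacement need not come from the same laboratory. Nobody independent checks the choice, and no analysis with the default baseline is planned. Assuming that the primary investigator of Section 6.3.1 is the principal investigator of Section 7.4.1, the person who can change the reference value also reviews response.

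The confirmation requirement does not help. It guards against one low on-treatment reading, but both readings are divided by the same baseline, so a favourably high baseline lowers the bar for both.

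**Working it through.** **1. The plan's own figures.** Inputs from Section 8: n = 15, at least 4 responders, true rates 10% and 40%. With X binomial, P(X ≥ 4) = 1 − Σ C(15,k) pᵏ(1 − p)¹⁵⁻ᵏ for k = 0 to 3.

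- p = 0.10: 1 − (0.2059 + 0.3432 + 0.2669 + 0.1285) = 0.0556. The plan states 5.6%.
- p = 0.40: 0.9095. The plan states 90.9%.

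Both reproduce.

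**2. Sensitivity of the 5.6% to the response rate.** The same formula gives 9.6% at a true rate of 12%, 17.7% at 15% and 35.2% at 20%. Small upward shifts in the per-patient rate matter.

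**3. What the choice of baseline can do to that rate.** The documents give no within-patient variability, so this step is an illustration on stated assumptions:

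- Each patient has two pre-treatment values and two on-treatment readings, log-normal, with independent deviations of SD √ln(1 + CV²) on the log scale. The CV is assumed to be 10% to 40%.
- The true log change varies between patients with SD 0.4 or 0.6 (assumed).
- A response requires both on-treatment readings at or below half the baseline.
- The mean change is set so that exactly 10% respond when the most recent value is the baseline. The whole 10% is thus attributed to calcitonin.

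One million patients were simulated per scenario, and the resulting rate was put into the binomial formula.

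| Assumed CV | Response rate, higher of two values (SD 0.4 / 0.6) | P(≥ 4 of 15) (SD 0.4 / 0.6) |
|---|---|---|
| 10% | 12.4% / 11.6% | 10.4% / 8.7% |
| 20% | 14.1% / 13.0% | 15.0% / 12.0% |
| 30% | 15.2% / 14.0% | 18.5% / 14.9% |
| 40% | 15.9% / 14.8% | 20.5% / 17.2% |

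If the other value is used for a reason unrelated to its size, the rate stays at 10.0% to 10.1% and P(≥ 4 of 15) at 5.5% to 5.6%. Replacement as such does no harm. Replacement that depends on which value is higher does, and it needs no knowledge of the outcome.

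**4. Does the text fix the timing of the decision?** On the plain reading of the opening sentence, yes. Three points keep that from being verifiable:

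- What is established before treatment could be the sample rather than the decision about it.
- The reference to enrollment in the sentence about the note can attach to the note or to the discarded value, so the note has no clear date.
- The 8-week window has no direction. Treatment starts on or near the enrollment day, so only the opening sentence keeps the window from reaching into treatment.

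**5. Which value is the default?** Under Section 6.3.1 it is the cycle 1 day 1 value where one is drawn. Under Section 2.5, or where footnote 5 is used, it is the screening value. The sections do not settle this.

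**The case against.** The strongest reply is that Section 6.3.1 already contains the safeguard. The baseline is to be set before treatment and a note must explain any departure, so a later choice would be a protocol deviation. That stands. A reader might infer that the plan lets the baseline be picked with the outcome in view; the documents do not support this.

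Two further inferences also fail. One is that an override can only be decided after dosing. The laboratory turnaround time is not given, screening values may serve for day 1, and a specimen problem can be known at the draw. Even a day 1 result returned after the first dose precedes the first on-treatment value at cycle 2, 21 days (± 7) later. The other is that the replacement must be older than the 10-day screening draw. An 8-week window includes that draw.

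A third reply is that little is at stake: this is a pilot, 4 of 15 is worded as an indication rather than a strict gate, and Section 8 adds a confidence interval and the individual decline percentages. This has weight, but those percentages would be computed from the designated baseline and would not show what the default would have given. One could also note that if a single non-responder per cohort could always be converted, 3 of 15 would suffice, with probability 18.4% at a true rate of 10%. That requires a convertible patient in every cohort, so it is not an estimate.

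Finally, an override used honestly in both directions can improve a poor baseline. That argues for keeping one, on objective grounds.

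**Conclusion.** The point holds in a limited form. The plan intends a pre-treatment baseline and requires a note, but it leaves replacement to a subjective judgement in an open-label trial. There is no objective ground, no selection rule, no dated lock and no default-baseline analysis. A choice informed by outcome is not authorised, but neither is it verifiably prevented, and a choice made before treatment can still favour the higher value.

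In the worst case, where the higher of two pre-treatment values is used for every patient, the 10% null rate becomes about 12% to 16% and the chance of 4 or more in 15 about 9% to 20%, against the stated 5.6%. These figures rest on an assumed CV of 10% to 40%, an assumed spread of true change, and a null rate made up wholly of calcitonin responses. Occasional overrides would have a smaller effect. The imaging component is untouched, and nothing in the documents shows that a baseline was chosen improperly.

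**What to change.** In Section 6.3.1, replace the subjective exception with text to this effect:

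*The baseline may be replaced only for a reason documented by the laboratory, such as specimen or assay failure. The replacement is the most recent other valid pre-dose value from the same laboratory. The choice and its reason are dated and locked before any post-dose calcitonin result is available.*

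State what happens if no such value exists. Reconcile Section 2.5 with Section 6.3.1, so that it is clear whether the default is the screening or the cycle 1 day 1 value when both exist. In Section 8, add the primary proportion for each cohort with the default baseline used for every patient, and list any overrides.

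The cost is a short edit to Section 6.3.1, a matching edit to Section 2.5 and one extra tabulation. Sample size, the cut-off of 4 and the stated 5.6% and 90.9% do not change. The downside is that a doubtful baseline without a laboratory reason stays in the main analysis.
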